9.2.2 Overall Survival

OS is defined as the time from the date of first dose until death due to any cause.

$OS \text{ (months)} = (\text{Death date or censor date} - \text{date of first dose} + 1) / 30.4375.$

Any patient not known to have died at the time of analysis will be right-censored based on the last recorded date on which the patient was known to be alive, i.e. the latest of (i) the “Date of study completion” (for those patients still alive) on the End of Study eCRF page and (ii) the “Date patient last known to be alive” on the Survival Follow Up eCRF page.”

The OS will be treated similarly to PFS. Median OS time and the proportion of patients who are alive at 3, 6, 9 and 12 months will be estimated. OS will be presented graphically using Kaplan-Meier plots by overall and Synovial cohort for the FAS and PPS in Phase II. To note, the 95% confidence interval will be calculated using “conftype = loglog” option within the Proc Lifetest procedure in SAS software.

OS will be listed by patient.

10 Pharmacokinetics, Immunogenicity and Pharmacodynamics

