6.19 Study Discontinuation

The reasons for discontinuing individual patients from further participation the study include:

- Patient death
- Patient lost to follow-up
- Patient withdraws consent for any further participation in the study including further participation in Survival Follow-Up
- End of the study is reached (see [Section 3.6](#))

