7.2 Treatment Period Schedule

The treatment period starts with Day 1 of Cycle 1 (C1D1). A treatment cycle is defined as 28 days for the purposes of scheduling procedures and evaluations.

Any assessments required on C1D1 that are also performed as part of Screening do not need to be repeated on C1D1 if the data were obtained 72 hours prior to the first dose of study treatment. For subsequent visits, pregnancy testing may be performed up to 72 hours prior to dosing and other safety assessments may be performed up to 24 hours prior to dosing.

During the study visits, all tests and/or procedures should occur on schedule whenever possible. A visit window of ± 7 days (with a minimum of 7 days between doses of IMCnyeso) is allowed unless otherwise indicated in the protocol. If study drug infusions are delayed, the assessments associated with those infusions should be rescheduled accordingly. However, the timing of protocol-specified radiological assessments should be calculated in weeks using C1D1 as reference and should not be adjusted because of delays in treatment.

Assessments required during the treatment period are presented by visit in [Table 7-2](#). For patients receiving IPE, follow the alternate Cycle 1 schedule provided in [Section 13.4](#). Assessments marked “X” should be performed prior to dosing. Assessments that are to be performed at multiple timepoints are marked with the number of timepoints (including optional timepoints, if applicable) for the visit (eg, 2 \times is twice) and details of the timepoints are provided in the footnote. Additional details regarding the assessments are provided in [Section 7.4](#). Please refer to [Section 6](#) for dosing details. Patients will continue treatment until they meet criteria for discontinuation, as described in [Section 6.16](#).

Table 7-2: Schedule of Treatment Period Assessments

Procedure	Cycle 1						Cycle 2				Cycle 3				Later Cycles			
Day of Cycle	1	2	8	9	15	22	1	8	15	22	1	8	15	22	Visits on Days 1, 8, 15, and 22			
Adverse events	X	X	X	X	X	X	X	X	X	X	X	X	X	X		X		
Concomitant medications	X	X	X	X	X	X	X	X	X	X	X	X	X	X		X		
Safety Assessments																		
Complete physical examination	X																	
Abbreviated physical examination			X		X	X	X	X	X	X	X	X	X	X		D1 of each cycle		
Weight	X						X				X						D1 of each cycle	
Vital signs	~14x	~14x		3x	3x	3x	3x	3x	3x	3x	3x	3x	3x	3x		3x each dosing day		
12-lead ECG (single)	2x						2x				2x					2x on C4D1, C5D1, and C6D1		

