Survival Follow-Up Period: Patients will be followed for survival every 3 months (may be done by telephone call) until death or until the end of the study is reached, unless they withdraw consent or are lost to follow-up. For patients whose status is unclear because they fail to appear for study visits without stating an intention to withdraw consent, the Investigator should show "due diligence" by contacting the patient, family, or family physician as agreed in the informed consent. The Investigator should record in the source documents the steps taken to contact the patient, eg, dates of telephone calls, registered letters, etc. A patient should not be considered lost to follow-up until due diligence has been completed. Patients lost to follow-up should be recorded as such on the appropriate Patient Disposition eCRF.

Assessments required as part of the study are presented by visit in [Table 7-3](#). A visit window of ± 14 days is allowed during follow-up.

Table 7-3: Schedule of Follow-Up Assessments

Procedure	EOT	30 days post last dose	90 days post last dose then Q3M
All Patients			
Survival contact		X	X
Subsequent anti-cancer treatment	X	X	X
Patients in Safety Follow-Up			
Adverse events	X	X	
Concomitant medications	X	X	
Abbreviated physical examination	X	X	
Weight	X	X	
Vital signs	X	X	
12-lead ECG (single)	X	Only if abnormal at EOT	
ECOG performance status	X	X	
Hematology panel	X	X	
Chemistry panel	X	X	
Coagulation	X	Only if abnormal at EOT	
Urinalysis	X	Only if abnormal at EOT	
Thyroid function	X	Only if abnormal at EOT	
Pregnancy test (serum or urine, women of childbearing potential)	X	X	
Immunogenicity	X		
Patients in Disease Progression Follow-Up			
CT/MRI scans and disease assessment	Q8W to Week 40 (post C1D1) then Q12W		
Tumor biopsy (optional)	Recommended at time of progression		

CT = computed tomography; ECG = electrocardiogram; ECOG = Eastern Cooperative Oncology Group; EOT = End of Treatment; MRI = magnetic resonance imaging; PK = pharmacokinetics; Q3M = every 3 months.

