9.2 Secondary Efficacy Endpoints

9.2.1 Progression-free Survival

PFS is defined as the time from first dose until the date of objective progression, or death from any cause, whichever occurs first. Patients who progressed or died immediately after two or more missed scheduled tumor assessments will be censored at date of last adequate assessment with evidence of no progression. Patients who have not progressed or died at the time of analysis will be censored at the time of the latest date of assessment from their last evaluable RECIST 1.1 assessment. These censoring rules apply regardless of what concomitant medications may have been taken or if the patient discontinued treatment prior to their last assessment. A sensitivity

analysis may be performed if subjects without objective disease progression receive a new anti-cancer therapy potentially affecting their results. In this analysis such patients will then be censored at the date of the last adequate response assessment prior to the new anti-cancer therapy.

$PFS \text{ (months)} = (\text{Event date} - \text{date of first dose} + 1) / 30.4375$

The PFS will be presented graphically using Kaplan-Meier plots including all patients treated at the MTD or RP2D and by overall and Synovial cohort. Median PFS time and the proportion of patients who are progression-free at 3, 6, 9 and 12 months will be estimated for each group. To note, the 95% confidence interval will be calculated using “conftype = loglog” option within the Proc Lifetest procedure in SAS software.

PFS per RECIST v.1.1 will be listed by patient and tabulated.

PFS per RECIST v.1.1 will be repeated for the PPS for Phase II.

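### The overall survival censoring rule in SAP 9.2.2 takes its date from two eCRF pages that are not scheduled for living patients still on treatment, so read literally it gives them no censor date

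*SAP*

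**What the plan says.** SAP 9.2.2 opens with a rule that has no exceptions: "Any patient not known to have died at the time of analysis will be right-censored". In full, such a patient "will be right-censored based on the last recorded date on which the patient was known to be alive, i.e. the latest of (i". The i.e. clause then defines that date as the later of two fields: the study completion date on the End of Study page (for patients still alive), and the last-known-alive date "on the Survival Follow Up eCRF page". No dosing, visit, laboratory, scan or cut-off date is named. SAP 4 adds that missing data are not imputed unless a later section says so, and 9.2.2 gives no fallback.

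The protocol determines when those pages would be expected:

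- **Treatment period (7.2).** "Assessments required during the treatment period are presented by visit in" Table 7-2, whose readable rows include no survival contact.
- **Follow-up (7.3, Table 7-3).** Survival contact is blank at the end-of-treatment visit. It is first marked at "30 days post last dose", then at 90 days and every 3 months.
- **Leaving the study (6.19).** The reasons are death, loss to follow-up, withdrawal of consent, or "End of the study is reached". Under 3.6 the planned end of study requires that all patients have completed treatment and safety follow-up.

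SAP 1 plans three deliveries. The Phase I Summary Report is cut once the MTD/RP2D is determined and DLT evaluation is complete. The full CSR is cut when at least 80% of each Phase II cohort have completed progression follow-up or left the study. The abbreviated CSR follows 100% follow-up.

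**The concern.** The opening rule covers every living patient, but the two sources that define its date do not. A living patient on weekly dosing at a cut has no scheduled Survival Follow Up page and no reason to have an End of Study page. The same holds for a patient between the last dose and the first survival contact. The SAP expects patients on treatment at a cut, because its disposition table (5.1) counts them.

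The OS formula needs a death date or a censor date. With neither, a patient has no OS time and cannot enter a Kaplan-Meier estimate. The patients exposed are all alive, so losing them would push the estimate in one direction only. Two programmers could also reach different denominators from the same paragraph, one following its opening sentence and the other its list. The outputs concerned are median OS and the proportions alive at 3, 6, 9 and 12 months.

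**Working it through.** **Step 1. Which patients have a date under the two-page list?**

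| Patient at the cut | End of Study page expected? | Survival Follow Up page scheduled? |
|---|---|---|
| Alive, on treatment | No (6.19, 3.6) | No (Table 7-2) |
| Alive, off treatment, before the 30-day contact | No | Not yet (Table 7-3) |
| Alive, past the 30-day contact | No, unless the patient has left the study | Yes |
| Alive at end of study | Yes | Yes |

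The gap is confined to the first two rows.

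**Step 2. Which deliveries are exposed?**

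- The full CSR is exposed, since up to 20% of a cohort may not have completed progression follow-up.
- Any Phase I report that carries the OS outputs listed in SAP 14.2 is exposed too. The SAP does not assign those outputs to a delivery. Protocol 9.1 places Phase I reporting after at least 6 cycles or treatment discontinuation for all Phase I patients.
- The abbreviated CSR after 100% follow-up is not exposed.

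**Step 3. How many patients?** 80% of 24 is 19.2, so at least 20 must have completed and up to 4 need not have. 80% of 9 is 7.2, so at least 8 must have completed and up to 1 need not have. I use 1 and 4 for illustration. Some of the 4 may be off treatment and already have survival contacts. Conversely, dosing may continue past progression under protocol 6.18, so 4 is not a strict limit.

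**Step 4. Direction.** A living patient censored at time c adds one to the number at risk at every death before c. Each such factor is 1 − 1/n with the patient and 1 − 1/(n − 1) without. The second is smaller, so removal can lower the estimate and never raise it.

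**Step 5. Size.** The plan states no survival assumption, so there is no plan figure to reproduce. Assume 24 patients, deaths at 0.5, 1.5, ..., 11.5 months (12 deaths), and 12 survivors. Of the survivors, k are last known alive at c months and the rest are followed past 12 months. Let m be the number of deaths before c.

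- Kept and censored at c: S(12) = (24 − m)/24 × (12 − k)/(24 − m − k)
- Removed: S(12) = (12 − k)/(24 − k)

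For k = 4, removal gives 8/20 = 40.0%. For k = 1 it gives 11/23 = 47.8%.

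| c (months) | m | Kept, k = 4 | Fall, k = 4 | Kept, k = 1 | Fall, k = 1 |
|---|---|---|---|---|---|
| 3 | 3 | 21/24 × 8/17 = 41.2% | 1.2 points | 21/24 × 11/20 = 48.1% | 0.3 points |
| 6 | 6 | 18/24 × 8/14 = 42.9% | 2.9 points | 18/24 × 11/17 = 48.5% | 0.7 points |
| 9 | 9 | 15/24 × 8/11 = 45.5% | 5.5 points | 15/24 × 11/14 = 49.1% | 1.3 points |
| over 12 | 12 | 12/24 = 50.0% | 10.0 points | 12/24 = 50.0% | 2.2 points |

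For scale, the exact 95% interval for 12/24 is 29.1% to 70.9%.

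**The case against.** The strongest reply is that the SAP already states the right principle. Its opening sentence covers everyone, and dropping a living patient would breach it. The harm needs a programmer to follow the explanatory list against the rule it explains. That is fair as to intent, but the list is introduced by i.e. and so reads as the definition. It is the part a programmer would code.

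The second reply is that visit schedules do not show which eCRF pages are completed at a data cut. The eCRF and its completion guidelines are not among the documents. A guideline or a survival sweep at the cut could supply a date for every ongoing patient. This stands: the documents show an incomplete rule, not that dates will be missing. Neither remedy is described, however.

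The third reply concerns weight. SAP 4 plans no hypothesis tests, OS does not enter the Simon rule, and the shift is well inside the sampling error. All of this stands.

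A reader might also infer more than the text supports:

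- **That the SAP instructs exclusion of on-treatment patients.** It does not. Loss of these patients is a risk of literal programming.
- **That the rule contradicts "The OS will be treated similarly to PFS".** That sentence introduces medians, landmark proportions, plots and confidence limits, so it concerns estimation and display. OS has its own censoring rule just above it. The PFS rule ("Patients who have not progressed or died at the time of analysis will be censored at the time of the latest date of assessment") does draw on scans taken during treatment, but it too states no fallback for a patient not yet scanned.
- **That the rule contradicts the Full Analysis Set definition (SAP 4.3.2).** That definition says who is analysed, and nothing in 9.2.2 removes anyone from it.

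**Conclusion.** The point holds as a specification fault of modest consequence. As worded, the i.e. clause gives no censor date to living patients who are on treatment or short of their first survival contact. If coded literally at a cut before full follow-up, it could bias OS downward.

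The likely size is 0.3 to 1.3 points of 12-month OS for one patient dropped from a cohort of 24, and 1.2 to 5.5 points for four, when they had been followed for 3 to 9 months. The 10-point figure needs all four to have been followed beyond 12 months and should not be read as the expected effect. These figures rest on assumed death times, an assumed 50% survival at 12 months and assumed numbers dropped. The conclusion also assumes that neither page is completed for ongoing patients at the cut, which only the eCRF guidelines could confirm. OS is secondary and descriptive, and the report after 100% follow-up is unaffected.

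**What to change.** In SAP 9.2.2, replace the i.e. clause so that the censor date is: *the latest date on or before the data cut-off at which the patient is documented alive in any eCRF or vendor record (including dosing, visit, laboratory, vital signs, tumor assessment, end of treatment, survival follow-up and end of study)*. Every treated patient then has an OS time at every cut.

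The cost is one clause and a standard last-known-alive derivation. It needs no new data and no change to study conduct. It should be in place before the first cut that reports OS.

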10.1 Pharmacokinetics

The PK analysis set will be used for all PK summaries and listings. All analyses will be reported in the clinical study report (CSR) and/or a stand-alone report. The following summaries/analyses will be provided for PK concentration data:

- Listings of IMCnyeso concentrations by cohort, visits and nominal timepoint.
- Plot of average pre-dose concentrations versus End of infusion at Day 1 of each Cycle.
- Summary of descriptive statistics of IMCnyeso PK concentrations by nominal time point in pg/mL.
 - The statistics to be presented include the n, arithmetic and geometric mean, median, standard deviation (Std), coefficient of variation (%CV), minimum, and maximum.
- Concentration profile plots for individual patients by Phase and cohort.
- Arithmetic mean concentration profile plots by Phase and cohort (colored line for each cohort/expansion) with errors bars (SD).

For calculating summary statistics, the following considerations will be taken into account:

- Concentration values below lower limit of quantitation (LLOQ) will be handled as zero in summary statistics. Values <LLOQ will be reported as is in the data listing of collected PK concentrations. The LLOQ for IMCnyeso is 25 pg/mL.
- If the arithmetic mean is below the LLOQ value (i.e. < 25 pg/mL) then the arithmetic mean will be displayed as '<LLOQ' in the summary table. The same holds for the following statistics: min, max, and median. The standard deviation and %CV will be reported as Not Calculable (NC).
- Concentration values and arithmetic means that are below the LLOQ value will be set to 12.5 pg/mL (half the LLOQ value) for display purposes in the both the individual concentration profiles and arithmetic mean profile plots.
- The geometric mean will be calculated as the exponential of the arithmetic mean calculated from data on a natural log scale. The geometric mean will only be calculated at timepoints where all patients have concentration values above the LLOQ (i.e. the min is >LLOQ).
- The %CV is calculated as $(\text{arithmetic standard deviation} / \text{arithmetic mean}) \times 100$.

Pharmacokinetic parameters will be calculated by non-compartmental methods utilizing Phoenix WinNonlin (Certa version 8.2 or higher, Princeton, NJ, US) utilizing the linear/log trapezoidal methods. For parameter calculations, concentration values reported as LLOQ at pre-dose will be treated as zero (0), all other timepoints reported as LLOQ will be treated as missing. The following PK parameters will be calculated for individual patients where possible:

Cycle 1 Day 1

- T_{max} – time to maximum concentration observed
- C_{max} – maximum concentration observed
- AUC_{last} – area under the concentration time profile from pre-dose to last measurable concentration

Cycle 1 Day 8

- T_{max} – time to maximum concentration observed
- C_{max} – maximum concentration observed
- AUC_{tau} – area under the concentration time profile over the dosing interval

Cycle 1 Day 15

- T_{max} – time to maximum concentration observed
- C_{max} – maximum concentration observed
- AUC_{tau} – area under the concentration time profile over the dosing interval

Additional PK parameters may be calculated as the analysts determines meaningful at the time of the analysis (e.g. clearance [CL], terminal elimination half-life [t_{1/2}], steady state volume of distribution [V_{ss}], etc.)

The following summaries/analyses will be provided for PK parameters:

- Listings of pharmacokinetic parameters by cohort and dose (Cycle and Day).
- Summary of descriptive statistics of IMCnyeso PK parameters by cohort and dose

- The statistics to be presented include the n, arithmetic and geometric mean, median, standard deviation (Std), coefficient of variation (%CV), minimum, and maximum.

Any missing PK parameter data will not be imputed.

10.2 Immunogenicity

Anti-drug Antibody (ADA) analysis will be used to evaluate immunogenicity responses. The frequency of ADA at baseline and following treatment will be summarized. All analyses will be reported in the CSR and/or a stand-alone report.

Sample ADA values at each visit and time-point will be collected in the following formats, from a third-party vendor:

- Binding ADA result
 - Positive: Final result in sample results spreadsheet (SRS) is Positive
 - Negative: Final result in SRS is Negative and PK value is < drug tolerance limit of assay (200 ng/mL, which is equivalent to 200,000 pg/mL)
 - Inconclusive: Final result in SRS is Negative and PK value is \geq drug tolerance limit of assay (200 ng/mL, which is equivalent to 200,000 pg/mL) or unknown
 - Unevaluable: Sample was unable to be analyzed (insufficient volume, wrong matrix, etc.)
- Binding ADA Titer value

Missing ADA values will be reported as is in data listings, as ‘No Result’ or ‘No Sample’.

For each patient, the final ADA status (derived from the cumulative ADA sample results for that patient) will be summarized. This will include:

- ADA status (Unevaluable, Positive, Negative)
- ADA Characterization (Treatment-induced, Treatment-boosted, or Pre-existing ADA)
- Time to ADA Onset for treatment-induced ADA patients
- ADA Duration category (Transient ADA response or Persistent ADA response)
- Max titer for treatment-induced ADA patients
- Peak fold increase in titer for treatment-boosted ADA patients

At a study level, the ADA data summaries will include:

- The number (%) of patients who are ADA-positive at baseline – see ADA *prevalence* at Baseline definition below.
- The number (%) of evaluable patients – see ADA Evaluable Subset definition below.
- The number (%) of patients who are ADA-positive at follow-up – see Overall ADA *incidence* definition below.
- The number (%) of patients who are ADA-negative at follow-up - see ADA Negative Subjects definition below.
- The number (%) patients with a treatment-induced ADA (from baseline negative) – see Treatment-induced ADA *incidence* definition below.

- The number (%) patients with a treatment-boosted (≥ 4 -fold) (from baseline positive) - see Treatment-boosted (≥ 4 -fold) ADA *incidence* definition below.
- The max titer from patients with treatment-induced ADA. Descriptive statistics including the median, IQR of the max titer will also be shown.
- The peak fold increase in titer among patients with treatment-boosted (≥ 4 -fold) ADA. Descriptive statistics including the median, IQR of peak titer fold increases will also be shown.
- A graphical representation of time to ADA onset and ADA duration for patients with treatment-induced ADA. Descriptive statistics (median, minimum and maximum) may also be summarized for time to ADA onset and ADA duration.

The following table gives the variables that will be derived for the binding ADA results and titers.

Variable	Definition
Baseline ADA result & Baseline ADA titer	See Section 9.6.3 of the protocol V4.0
Pre-existing ADA	Subject with Positive baseline ADA result (without a boost in titer in response to study drug administration). See below for definition of Treatment-boosted (≥ 4 -fold) ADA.
ADA prevalence at Baseline	The number of subjects with a Positive ADA result at baseline as a percentage of the total number of subjects tested at baseline for ADA.
ADA Evaluable Subset	All subjects who received at least one dose of study drug and have at least one ADA assessment post-baseline. This subset of the SAF will be used for determining ADA incidence.
Max titer	Highest titer value post-baseline.
Peak (or max) fold increase in titer	Ratio of max post-baseline titer to baseline titer (calculated only for subjects with a Positive ADA result at baseline).
Treatment-induced ADA	Subject in the ADA Evaluable Subset who has a positive ADA sample post-baseline with a Negative ADA result at baseline.
Treatment-induced ADA Incidence	Number of treatment-induced ADA subjects / Number of subjects in ADA Evaluable Subset with a Negative ADA result at baseline.
Treatment-boosted (≥ 4 -	Subject in the ADA Evaluable Subset who has a Positive

fold) ADA	ADA sample at baseline and a Positive ADA sample post-baseline with a titer that has a peak (or max) fold increase in titer ≥ 4 compared to baseline.
Treatment-boosted (≥ 4 -fold) ADA incidence	Number of treatment-boosted (≥ 4 -fold) ADA subjects / Number of subjects in ADA Evaluable Subset with a Positive ADA result at baseline.
Overall ADA Incidence (ADA Positive Subjects)	All subjects with a treatment-induced or treatment-boosted ADA response (see definitions above) or subjects with positive post-baseline ADA sample but do not have a baseline ADA sample in the ADA Evaluable Subset.
ADA Negative Subjects	All subjects without a treatment-induced nor treatment-boosted ADA response in the ADA Evaluable Subset (can include subjects classified as Pre-existing ADA).
ADA Status	Three categories: 
 a. Unevaluable: Patient has no post-baseline ADA samples. b. Positive: See “ADA Incidence (ADA Positive Subjects)” definition above. c. Negative: See “ADA Negative Subjects” definition above (can include subjects classified as Pre-existing ADA).
ADA Onset (as applicable)	For subjects with a treatment-induced ADA response: number of days from first dose of study drug to the first instance of Positive ADA. 
Therefore, ADA Onset = (date of first instance of Positive ADA – date of first dose of study drug + 1).

ADA Duration (as applicable)	For subjects with a treatment-induced ADA response: number of days from the first instance of Positive ADA to last instance of Positive ADA for a subject, such that a subsequent Negative ADA follows the last instance of Positive ADA. 
Therefore, ADA Duration = (date of last Positive ADA* – date of first instance of Positive ADA + 1).
 
*The last Positive has to exist such that a Negative ADA follows the last instance of Positive ADA. If the date of last Positive ADA result is the final ADA assessment, then ADA duration will be calculated above, but in this case, the duration will be concatenated with '+' to imply that the ADA duration is at least the calculated number of days.

Transient ADA response	ADA Positive subject (post-baseline) with at least one subsequent Negative result, after the last Positive result and the ADA Duration is < 20 weeks (i.e. < 140 days).
Persistent ADA response	Subject with either (i) an ADA Duration \geq 20 weeks (i.e. \geq 140 days), regardless of whether intervening sample results are Positive or Negative; or (ii) if last sample is ADA Positive (i.e. where ADA Duration is concatenated with '+' as described above).

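### SAP 10.2 classes a post-baseline ADA-positive patient with an unusable baseline sample as ADA-negative, and leaves two other patient types wrongly or doubly classified

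*SAP*

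**What the plan says.** SAP 10.2 sorts each sample as Positive, Negative, Inconclusive or Unevaluable.

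- **Inconclusive** covers a screen-negative sample whose drug level is too high or not known: "Inconclusive: Final result in SRS is Negative and PK value is" at or above the "drug tolerance limit of assay (200 ng/mL, which is equivalent to 200,000 pg/mL) or unknown".
- **Unevaluable**, at sample level, means that the sample could not be run: "Unevaluable: Sample was unable to be analyzed (insufficient volume, wrong matrix, etc".

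At patient level there are only three statuses: "ADA status (Unevaluable, Positive, Negative". The derived-variable table gives the rules.

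- **ADA Evaluable Subset:** "All subjects who received at least one dose of study drug and have at least one ADA assessment post-baseline". The table adds: "This subset of the SAF will be used for determining ADA incidence".
- **Treatment-induced:** "Subject in the ADA Evaluable Subset who has a positive ADA sample post-baseline with a Negative ADA result at baseline".
- **Treatment-boosted:** a Positive baseline sample and a later titer at least 4-fold higher.
- **ADA Positive:** induced, or boosted, or Positive after baseline in a patient who has no baseline sample.
- **ADA Negative:** "All subjects without a treatment-induced nor treatment-boosted ADA response in the ADA Evaluable Subset".
- **Unevaluable status:** only a patient with no post-baseline sample at all.

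For the baseline ADA result the table points to protocol Section 9.6.3. That section says only that ADA frequency at baseline and after treatment will be summarized.

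**The concern.** Negative is defined by exclusion, from a population that does not require a usable result. A patient about whom nothing conclusive is known can therefore be reported as ADA-negative, although at sample level the SAP declines to call the same result Negative. More seriously, a patient with a Positive post-baseline sample can be reported as ADA-negative because of a fault in the baseline sample.

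ADA incidence is a secondary endpoint in both phases (protocol Table 4-1; SAP 3.2.2), and the protocol also lists the impact of ADA on PK. A positive patient placed in the negative group lowers the incidence and blurs any ADA-by-PK comparison. Where the definitions overlap, two programmers could produce different tables from the same data.

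**Working it through.** The documents state no ADA incidence figure, so there is nothing to reproduce. The check applies the definitions literally to each pairing of baseline result (Positive, Negative, Inconclusive, Unevaluable, no sample) with post-baseline result.

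| Case | Baseline | Post-baseline | Induced? | Boosted? | Positive via no baseline sample? | Status as written |
|---|---|---|---|---|---|---|
| 1 | Inconclusive or Unevaluable | Positive | No, baseline is not Negative | No, baseline is not Positive | No, a sample exists | Negative |
| 2 | No sample | Positive | No | No | Yes | Positive and Negative |
| 3a | Any | Inconclusive only | No | No | No | Negative |
| 3b | Any | Unevaluable only | No | No | No | Negative if a collected sample counts as an assessment; otherwise none of the three statuses fits |

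Other pairings give one defensible answer. A Negative baseline with any later Positive is Positive. A Positive baseline with a rise below 4-fold is Negative by the SAP's stated treatment of pre-existing ADA.

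**Could an earlier sample replace an unusable baseline?** The visible rows of protocol Table 7-1 show no screening ADA sample, and Table 7-2 starts ADA sampling at C1D1. No scheduled substitute is shown.

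**How could a result become Inconclusive?** Dividing dose by the protocol's assumed volume of 8 L (Section 6.9) gives a peak for the highest listed dose, 300 mcg (SAP Table 1), of 300 mcg / 8 L = 37.5 ng/mL. Against the 200 ng/mL limit that is 37.5/200 = 18.75%. High drug concentration is therefore an unlikely cause, and an unknown PK value is the likelier one.

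**Direction.** Using the Evaluable Subset as the denominator of overall incidence, cases 1 and 3 can enter the denominator but never the numerator. Treatment-induced and treatment-boosted incidence are diluted by case 3. Case 1 lies outside the numerators and denominators of both.

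**Size, by illustration.** SAP Table 1 gives 4+3+5+3+5+4+6 = 30 Phase I patients, the last 6 planned. Assume all 30 are in the subset and 6 are Positive under the SAP rules, so 6/30 = 20.0%. The counts below are assumed.

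- One case 1 patient counted as Positive: 7/30 = 23.3%, a shift of 1/30 = 3.3 points. In a full Phase II cohort of 24 it is 1/24 = 4.2 points.
- One case 3 patient removed: 6/29 = 20.7%. Three removed: 6/27 = 22.2%. Six removed: 6/24 = 25.0%.
- Three case 3 patients removed and one case 1 patient: 7/27 = 25.9% if that patient is counted Positive, 6/26 = 23.1% if excluded.
- No such patients: 20.0%, unchanged.

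**End-of-treatment (EOT) samples.** Protocol Table 7-3 schedules an ADA sample at EOT and has no PK row. Section 7.4.5 says that later PK sampling is taken pre-dose and at EOT. If no PK value is obtained, a screen-negative EOT sample is Inconclusive. When it directly follows the last Positive, the duration category also fails. There is no later Negative result, so the response is not transient. The last sample is not Positive, so the second persistent criterion fails. The duration itself has no defined end, so the first cannot be applied.

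**The case against.** The best counter-argument is that these patients should be rare. Every scheduled on-treatment ADA day (C1D1, C1D8, C1D15, C2D1, C3D1 and Day 1 of later odd cycles) has a paired pre-dose PK sample in Table 7-2, and the intra-patient escalation schedule in Table 13-13 does the same for its Cycle 1 ADA days. A patient dosed through C1D8 should therefore already have a conclusive post-baseline result unless a sample is lost or fails. Case 1 needs a lost PK value or unusable ADA sample at C1D1, followed by a Positive. In addition, at 37.5 ng/mL against 200 ng/mL, a screen-negative sample without a PK value is unlikely to conceal an antibody, so calling that patient Negative is often correct. The objective is only preliminary incidence, and no hypothesis is tested.

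Most of this stands, and it limits the size of the problem. It does not answer case 1, where the post-baseline sample is actually Positive, or case 2, where the definitions overlap. One could hope that a programmer would treat an unusable baseline as no baseline sample. However, the SAP separates a missing result from a missing sample in its listings, and its third route to Positive refers only to the sample.

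A reader might infer that every screen-negative EOT sample is affected and that the understatement is systematic. The documents do not support that. An Inconclusive EOT sample does not alter the status of a patient with an earlier valid Negative, and the two protocol passages conflict on whether PK is taken at EOT at all.

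**Conclusion.** The definitions, as written, misclassify case 1, double-classify case 2, and count case 3 as Negative. No other section corrects this. For Unevaluable samples, case 3 depends on the undefined meaning of an assessment; for Inconclusive samples there is no such doubt.

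Any error in overall incidence is downward. The documents give no counts, so neither a definite amount nor a definite understatement can be claimed, and the error is zero if no such patient arises. The 3.3-point figure should not be read across to all cases: it belongs to case 1 in Phase I and assumes 30 evaluable patients. A case 3 patient moves only the denominator, by 0.7 points in the one-patient illustration. The EOT route matters mainly for patients without an earlier conclusive post-baseline sample, such as those who stop before C1D8, and for the duration category when EOT directly follows the last Positive. This is a minor point of specification, worth settling before the ADA tables are programmed.

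**What to change.** In the SAP 10.2 table:

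1. Require at least one conclusive (Positive or Negative) post-baseline result for the ADA Evaluable Subset.
2. Widen Unevaluable status, or add an Inconclusive status, to cover patients without one, and report their number.
3. Count a post-baseline Positive whose baseline is missing, Inconclusive or Unevaluable as ADA-positive overall, shown apart from treatment-induced and treatment-boosted.
4. Define Negative as evaluable and not Positive, so that the classes cannot overlap.
5. Define the baseline ADA result in the SAP itself, in place of the reference to protocol 9.6.3.
6. Reconcile protocol Table 7-3 with Section 7.4.5 on PK at EOT. State how a screen-negative EOT sample without a PK value is classed, including for the transient and persistent categories.

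The cost is wording in one SAP table and its status list, plus one protocol clarification. No new data are needed unless the reconciliation adds a PK sample at EOT.
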